| Study Phases | 
Phase I
 
 • Initial Screening • Visit 1 – Informed Consent, Ekman 60 Faces Test, PPVT • Visit 2 – Assessments and Surveys (Baseline) • Week 1 (following Visit 2) – Gameplay – daily transmission of game data • Week 1 – Survey – data transmission • Visit 3 – Assessments and Surveys • Week 2 – Gameplay – daily transmission of game data • Week 2 – Survey – data transmission • Visit 4 – Assessments and Surveys • Week 3 – Gameplay – daily transmission of game data • Week 3 – Survey – data transmission • Visit 5 – Assessments and Surveys • Week 4 – Gameplay – daily transmission of game data • Week 4 – Survey – data transmission • Visit 6 – Assessments and Surveys 
(Note: Phase II may not begin immediately following phase I)
 
Phase II
 
 • Week 1 – Gameplay – daily transmission of game data • Week 1 – Survey – data transmission • Visit 1 – Assessments and Surveys |

| | |
|--------------------------------------|--|
| | 
 • Week 2 – Gameplay – daily transmission of game data • Week 2 – Survey – data transmission • Visit 2 – Assessments and Surveys • Week 3 – Gameplay – daily transmission of game data • Week 3 – Survey – data transmission • Visit 3 – Assessments and Surveys • Week 4 – Gameplay– daily transmission of game data • Week 4 – Survey – data transmission • Visit 4 – Assessments and Surveys |
| Efficacy Evaluations | 
The primary efficacy endpoints will be:
 
The mean change from baseline score on the following assessments based on post-final game play session assessment compared to the alternate game group:
 
 a. Subject gaze patterns as measured by video eye tracking assessment. b. Subject gaze patterns as measured by the dyadic interaction task. c. Mean change in baseline score on the Ekman 60 Faces Test. d. Mean change in baseline score on the TOVA. e. Mean change in baseline score on the SRS. 
Secondary endpoints:
 
The mean change from baseline score on the following assessments based on post-final game play session assessment compared to the alternate game group:
 
 a. Subject gaze patterns as measured on the videos of emotional expression assessment. b. Subject responses to the CJARS survey. |
| Pharmacokinetic Evaluations | N/A |

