All written or electronic forms (except Informed Consent Forms and Assent Forms) will employ a unique alphanumeric identifier; in no case will the participant's name or other identifying information appear on these forms. The user ID for the BioStream Training and alternate game shall use the same unique alphanumeric identifier. The study team will accomplish this on all parent/guardian or teacher or therapist questionnaires (as applicable) which have lines for child and parent name by applying a label with unique alphanumeric identifier and instructing parents/guardians or teacher or therapists to use generic labels (e.g., biological mother) rather than writing their names. The PI will keep a master list containing PHI and subject ID number separate from coded data forms, which will be maintained in a locked file drawer, cabinet, or lock box in the PI's office. Only the PI will have access to this location. The master list will be maintained on a separate password-protected computer and be stored in an encrypted password protected file. Video recordings will stored on password-protected and/or encrypted data storage devices including computers, external hard drives, and/or flash drives only accessible by members of the study team.

**TABLE 1: SCHEDULE OF STUDY PROCEDURES
(INITIAL SCREENING)**

| | Estimated time | Parent or subject? |
|---|-----------------------|---------------------------|
| Informed Consent | 15 minutes | Parent |
| Review of Inclusion/Exclusion Criteria (Initial Screening Interview) | 15 minutes | Parent |
| Video Game Interview Form (Parent-Report) | 15 minutes | Parent |

**TABLE 2: PHASE I SCHEDULE OF STUDY PROCEDURES
(HOME, SCHOOL, THERAPY CENTER, OR RESEARCH ORGANIZATION)**

| | Estimated time (total over all visits) | Parent or subject? | Visits applicable (Total 6 Visits) |
|--|---|---------------------------|---|
| Informed Consent/Assent (if applicable) | 30 minutes | Parent and subject | Visit 1 |

| | | | |
|---|----------------------------------|----------------|--|
| Peabody Picture Vocabulary Test (PPVT) | 20 minutes | Subject | Visit 1 |
| Ekman 60 Faces Test | 10 minutes | Subject | Visit 1 |
| SRS (Parent-Report) | 50 minutes | Parent | Visits 2-6 |
| C-JARS (Parent-Report) | 50 minutes | Parent | Visits 2-6 |
| Dyadic Interaction Task | 50 minutes | Subject | Visits 2-6 |
| Eye Tracking Video Assessment | 50 minutes | Subject | Visits 2-6 |
| Ekman 60 Faces Test | 50 minutes | Subject | Visits 2-6 |

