| Emotional Expression Video Assessment | 50 minutes | Subject | Visits 2-6 |
| TOVA | 109 minutes | Subject | Visits 2-6 |
| Game and equipment introduction (if applicable) | 40-60 minutes | Parent | Visit 1 |
| BioStream Training | 6.67-33.33 hours | Subject | Over a period of 28 days following Visit 2 |
| Weekly Parental/Teacher/Therapist Survey | 20 minutes | Parent | 1 survey/per week |
| Subject Interview/Survey (if applicable) | 40 minutes | Subject | Visits 3 - 6 |
| Parent/Teacher/Therapist Interview/Survey (if applicable) | 40 minutes | Parent | Visits 3 - 6 |
| Equipment return (if applicable) | 5 minutes | Parent | Visit 6 |
| TOTAL | 13.48 hours – 41.15 hours | Subject | |
| TOTAL | ~4.25 hours* | Parent | *Excludes time spent for oversight of subject during BioStream Training |

**TABLE 3: PHASE II SCHEDULE OF STUDY PROCEDURES
(HOME, SCHOOL, THERAPY CENTER, OR RESEARCH ORGANIZATION)**

| | Estimated time (total over all visits) | Parent or subject? | Visits applicable (Total 4 Visits) |
|---------------------------------------|---|---------------------------|---|
| SRS (Parent-Report) | 40 minutes | Parent | All Visits |
| C-JARS (Parent-Report) | 40 minutes | Parent | All Visits |
| Dyadic Interaction Task | 40 minutes | Subject | All Visits |
| Eye Tracking Video Assessment | 40 minutes | Subject | All Visits |
| Ekman 60 Faces Test | 40 minutes | Subject | All Visits |
| Emotional Expression Video Assessment | 40 minutes | Subject | All Visits |
| TOVA | 87 minutes | Subject | All Visits |
| BioStream Training | 6.67-33.33 hours | Subject | Over a period of 28 |

| | | | |
|---|----------------------------------|----------------|--|
| | | | days |
| Weekly Parental/Teacher/Therapist Survey | 20 minutes | Parent | 1 survey/per week |
| Subject Interview/Survey (if applicable) | 40 minutes | Subject | All Visits |
| Parent/Teacher/Therapist Interview/Survey (if applicable) | 40 minutes | Parent | All Visits |
| Equipment return (if applicable). | 5 minutes | Parent | Visit 4 |
| TOTAL | 11.45 hours – 38.12 hours | Subject | |
| TOTAL | ~2.5 hours* | Parent | *Excludes time spent for oversight of subject during BioStream Training |

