3.1.1 Initial Screening

Potential subjects will be first screened by any study team member in an in-person or telephone interview with the parent/guardian. After written informed consent is obtained to the initial screening (in the case of an in-person interview) or verbal informed consent is obtained to the initial screening (in the case of a telephone interview), protocol inclusion and exclusion criteria will be reviewed with the parent/guardian. The parent/guardian will also be asked for a list of the medications the subject is currently taking and that information will be recorded. A subset of questions from the SRS will be asked as part of the screening. The parent/guardian will also be asked if the subject has a diagnosis of ADHD and if so, that will be noted.

Prospective Study Participant Initial Screening Form. This short questionnaire will be administered to the parent/guardian in-person or by telephone prior to the study visit to

query their children's video game playing habits. This questionnaire should take less than 15 minutes to complete. Questions related to the inclusion/exclusion criteria will also be asked to determine eligibility.

3.1.2 Phase I Visit 1

Parental/guardian permission (informed consent) and, if applicable, child assent, will be obtained. Subjects will participate in social skills assessments. The subject will participate in the Peabody Picture Vocabulary Test, 4th Edition [34]. If the study team member determines that the subject's intelligence standard score is below 40, then the subject will not be able to continue to be included in the study per the exclusion criteria (see page 4). The subject will participate in the Ekman 60 Faces Test. If the subject score is greater than 75% correct, then the subject will not be able to continue to be included in the study per the exclusion criteria.

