5.7.2 Efficacy Analysis

The primary analysis will be based on all subjects randomized at the initial visit for who initial visit and final visit data is collected.

Paired-sample t-tests will be used to measure changes from baseline within each group, and independent sample t-tests will be used to measure changes from baseline relative to the alternate game group for all endpoints.

For all endpoints, we will determine whether there were statistically significant changes in scores from baseline or relative to the alternate game group. Significance will be set at $p < 0.05$. Multiplicity of primary endpoints will be managed via statistical corrections.

Secondary endpoints will be evaluated in a similar manner. Analysis will include all subjects for who initial visit and final visit data is collected. The treatment and control groups will be compared using t-tests as described above.

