 - [34] L. Hoffman, J. Templin, and M. L. Rice, "Linking outcomes from peabody picture vocabulary test forms using item response models," *J Speech Lang Hear Res*, vol. 55, no. 3, pp. 754-63, Jun 2012.
-

ClinicalTrials.gov
Document Submission Cover Page

Official Title of Study: Computer-based Social Skills Training for Autism Spectrum Disorder

NCT Number of Study: NCT03672344

Unique Protocol ID: 08012018A

Document Title: Supplement to Statistical Analysis Plan

Document Date: April 25, 2022

Study Sponsor: BioStream Technologies, LLC

Supplement to Statistical Analysis Plan

In addition to the statistical analyses described in the original study protocol, a 2 (Time) × 2 (Condition) mixed ANOVA was conducted to test for between-group differences in Ekman-60 scores from pre- to post-intervention. Mixed ANOVAs also will be used to test for between-group differences in Social Responsiveness Scale (SRS) and Child Joint Attention Rating Scale (C-JARS) scores from pre- to post-intervention. Significance will be set at $p < 0.05$.

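### Two Ekman 60 scores are scheduled before gameplay, but the between-arm Ekman analysis uses at most one and adjusts for neither, giving up some precision

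*Combined protocol and SAP*

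**What the plan says.** The synopsis lists "Visit 1 – Informed Consent, Ekman 60 Faces Test, PPVT" and then "Visit 2 – Assessments and Surveys (Baseline"). Table 2 has two Ekman rows: "Ekman 60 Faces Test | 10 minutes | Subject | Visit 1" and "Ekman 60 Faces Test | 50 minutes | Subject | Visits 2-6". The 50 minutes match five sittings of 10 minutes, so Phase I has six sittings in all. Table 2 places the training period "Over a period of 28 days following Visit 2".

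The Visit 1 score decides eligibility. Section 3.1.2 reads "The subject will participate in the Ekman 60 Faces Test. If the subject score is greater than 75% correct", and such a child does not continue. No other primary endpoint is scheduled before Visit 2.

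On analysis, section 5.7.2 states that "independent sample t-tests will be used to measure changes from baseline relative to the alternate game group for all endpoints". Its analysis set is children randomised at the initial visit who have initial-visit and final-visit data. The April 2022 supplement reports that a two-by-two "mixed ANOVA was conducted to test for between-group differences in Ekman-60 scores from pre- to post-intervention". Neither text averages the two early scores or enters either as a covariate.

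**The concern.** A single 60-item test in children aged 4 to 14 carries measurement error, and a second score taken before treatment reduces it. Both scores are already scheduled, yet a change-score t-test can use only one of them. The mixed ANOVA recovers nothing, because with two time points its time-by-condition interaction is the change-score test in another form.

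At stake is precision on one of five primary endpoints, the one that the supplement takes up first. The documents also disagree on which score is the baseline: the synopsis labels Visit 2, while section 5.7.2 uses the initial visit, which on the schedule is Visit 1. If it is Visit 1, the baseline is the score capped at 75% correct by eligibility. The within-group paired test is then open to regression to the mean.

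**Working it through.** **The plan's own figure.** Section 5.8 gives up to 150 participants with no effect size, SD, correlation or power, so there is no calculation to reproduce.

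**Assumptions.** 1:1 allocation (75 per arm; the ratio is not stated), two-sided 0.05 without multiplicity correction, equal SD at each visit, and an effect for which the reference analysis has 80% power. Power is from the noncentral t. Two extra covariates take residual degrees of freedom from 150 − 2 = 148 to 150 − 4 = 146, which is negligible.

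**Equivalence check.** In simulated data with 75 per arm, the mixed ANOVA interaction F and the squared change-score t were both 6.875.

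**Case A: equal correlation ρ between any two scores, no entry cut.** Error variance in units of SD²:
- change from Visit 2: 2(1 − ρ)
- Visit 2 as covariate: 1 − ρ²
- Visits 1 and 2 as covariates: 1 − 2ρ²/(1 + ρ)

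| ρ | Change | Visit 2 covariate | Both | Both vs change: variance cut, power | Both vs Visit 2 covariate: variance cut, power |
|---|---|---|---|---|---|
| 0.5 | 1.000 | 0.750 | 0.667 | 33%, 80% → 92.9% | 11%, 80% → 84.4% |
| 0.7 | 0.600 | 0.510 | 0.424 | 29%, 80% → 91.5% | 17%, 80% → 86.7% |
| 0.8 | 0.400 | 0.360 | 0.289 | 28%, 80% → 90.9% | 20%, 80% → 87.8% |

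At ρ = 0.5, 25 of the 33 percentage points of variance cut come from the Visit 2 covariate alone.

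**Case B: Case A with the entry cut on Visit 1.** The documents do not say where 75% correct lies in the score distribution, so the cut was simulated at 0.5, 1.0 and 1.5 SD above the mean.
- Visit 1's own addition shrinks to +2.6 to +3.7 points at ρ = 0.5, +4.7 to +6.0 at 0.7 and +6.0 to +7.2 at 0.8.
- The total gain over a Visit 2 change score is unaffected.
- If the planned change is taken from Visit 1 instead, the total is smaller: 80% to between 89.3% and 91.5%.

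**Case C: correlation decays with time, no entry cut.** Let a, b, c be the correlations Visit 1–Visit 2, Visit 1–final and Visit 2–final. Error variance with both covariates is 1 − (b² + c² − 2abc)/(1 − a²). For 0.80/0.60/0.70 this is 1 − (0.36 + 0.49 − 0.672)/0.36 = 0.506, against 0.510 with Visit 2 alone and 0.600 for the change score.

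| a / b / c | Visit 1's own variance cut | Visit 1's own power gain | Total power gain over Visit 2 change |
|---|---|---|---|
| 0.80/0.60/0.70 | 1% | +0.3 | +6.3 |
| 0.70/0.50/0.60 | 2% | +0.8 | +8.6 |
| 0.80/0.70/0.80 | 3% | +1.1 | +5.0 |
| 0.80/0.65/0.70 | 4% | +1.7 | +7.5 |
| 0.75/0.65/0.70 | 7% | +2.8 | +8.3 |

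**Across the cases.** The total gain over the planned test is about +5 to +13 points. Visit 1's own addition is about 0 to +7 once the entry cut or decay is allowed for.

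**The case against.** The strongest reply is that a change-score t-test is valid under randomisation, that most of the gain is the general case for covariate adjustment, and that Visit 1 adds little. Much of this stands. Visits 1 and 2 are both untreated, whereas the final score follows 28 days of play. It may instead follow Phase II, which section 3.3.1 allows to end up to 16 weeks from enrolment. Some decay in correlation is therefore plausible, and in Case C Visit 1 then adds less than 3 points. Even so, the two-covariate model gains at least 5 points over the planned test in every case examined.

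A second objection is timing. The supplement reports the Ekman ANOVA as already carried out, so a new between-arm model may be a post hoc change to a primary endpoint. That stands, and it limits how the result can be presented.

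A third is that Visit 2 may not be wholly untreated. Section 3.1.3 has the training group undergo the game introduction, while Table 2 and section 4.2 direct it to the parent, teacher or therapist. If children play during it, the Visit 2 score follows some exposure. The passages must be reconciled.

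The entry cap is not a valid objection to the covariate. Selection on a score taken before treatment does not bias a randomised comparison.

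**Conclusion.** The point holds as a matter of efficiency. The between-arm Ekman analysis uses at most one of two scheduled pre-gameplay scores and adjusts for neither. The total gain available is about +5 to +13 power points, much of it from covariate adjustment. Visit 1's own share is about 0 to +7, reaching 5 or more only if correlations are equal and about 0.7 or higher. All of this rests on assumed correlations, equal SDs and 75 per arm.

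Three stronger readings are tempting, and the documents do not support them:
- **Every randomised child has two scores.** Section 5.7.2 places randomisation at the initial visit, so a child who leaves before Visit 2 has one.
- **The gain is above 10 points throughout.** It is +5 to +9 under decay, and can fall to about +9 if baseline is the capped Visit 1 score.
- **The planned test is biased or inflates type I error.** Nothing here shows that for the comparison between arms.

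**What to change.** In section 5.7.2 and the supplement:

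1. Specify the between-arm Ekman analysis as a linear model of the final-visit score on arm, with the Visit 1 and Visit 2 scores as two separate covariates.
2. State whether baseline is Visit 2, as in the synopsis, or the initial visit, as in section 5.7.2.
3. Do not average the capped Visit 1 score into the baseline of the within-group paired test, where it would bring in regression to the mean.
4. If the Ekman data have already been analysed, label the model post hoc, for example as a sensitivity analysis beside the reported ANOVA.

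The cost is SAP wording and one model term beyond a Visit 2 covariate, with no new visits or testing. The Ekman model would carry one more covariate than a baseline-adjusted model for any other endpoint, and after analysis it could not be presented as prespecified.

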| Study Objective(s) | 
Primary
 
To evaluate changes in subject performance on various social skills assessments (including eye-tracking, dyadic interaction, SRS, Ekman 60 Faces Test) after engaging in BioStream Training, including in comparison to an alternate game.
 
Secondary
 
To observe changes in subject gaze patterns during social skills assessments after engaging in BioStream Training, including in comparison to an alternate game.
 
To observe possible correlations in changes in social skills assessments with changes in subject gameplay performance.
 |
| Test Article(s) (If Applicable) | BioStream Training is computer-based social skills training that includes interactive game-like applications involving images, video, audio, and animation (e.g. animated characters). |
| Study Design | Comparison Group |
| Subject Population key criteria for Inclusion and Exclusion: | 
Inclusion Criteria
 
 1. Ages 4-14. 2. Meets diagnostic criteria for ASD. 3. Estimated intelligence standard score of at least 40 (can be substituted for a receptive language score such as PPVT or use |

of the Differential Ability Scales, 2nd Edition (DAS-II)).

4. Parent reports difficulty with at least one of two social skills (via modified questions from the Social Responsiveness Scale)
5. English as the child's primary/first language (key measures used in the study do not have alternate language versions).
6. Attains a score equal to or less than 75% correct on the Ekman 60 Faces Test.
7. The parent who completes the questionnaires needs to be proficient in English.
8. Has successfully played a video game using a Microsoft Xbox game controller, Sony PlayStation game controller, or other comparable game controller.
9. Parental/guardian permission (informed consent) and if appropriate, child assent.
10. Wi-Fi internet connection at subject's home/school/therapy center/research organization available for use by study laptop computer.

Exclusion Criteria

1. History of seizures.
 2. History of traumatic brain injury or other significant medical or neurological abnormality affecting motor or higher cortical functioning.
 3. Certain visual, auditory, DSM 5, or conduct disorders (see below).
 4. A visual disorder that cannot be corrected through the use of corrective lenses to a level of 20-40 in both eyes.

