| Safety Evaluations | 
Subjects will always be supervised by a parent, teacher, or therapist (therapist includes Registered Behavior Technicians, assistant speech pathologists, assistant behavior analysts (BCABA), and teaching assistants) during use of the BioStream training and alternative game. Clinical adverse events (AEs) will be monitored throughout the study through parent reporting in the case of at home use and through teacher reporting in the case of in school use. Since the study procedures are not greater than minimal risk, AEs are not expected.
 |
| Statistical And Analytic Plan | 
Paired-sample t-tests will be used to measure changes from baseline within each group, and independent sample t-tests will be used to measure changes from baseline relative to the alternate game group for all endpoints.
 |

For all endpoints, we will determine whether there were observable changes in scores from baseline or relative to the alternate game group and whether these changes are statistically significant. Significance will be set at $p < 0.05$. Multiplicity of primary endpoints will be managed via statistical corrections.

**DATA AND SAFETY
MONITORING PLAN**

The PI will periodically review the data collection and storage practices associated with this study and determine whether changes to enhance confidentiality and privacy are required. The PI will frequently monitor the quality control of the data with staff and research assistants.

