2 STUDY OBJECTIVES

2.1 Primary Objective (or Aim)

The primary objective of this study is to determine whether 6.67 to 33.33 hours of BioStream Training improves the performance of children with ASD on social skills assessments including in comparison to an alternate game. Specifically with respect to the following:

The mean change from baseline score on the following assessments based on post-final game play session assessment compared to the alternate game group:

- a. Subject gaze patterns as measured by video eye tracking assessment.
- b. Subject gaze patterns as measured by the dyadic interaction task.
- c. Mean change in baseline score on the Ekman 60 Faces Test.
- d. Mean change in baseline score on the TOVA.
- e. Mean change in baseline score on the SRS.

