3.1.4 Alternate Game Group

The alternate game group will undergo an estimated 40-60 minute training session on how to use the alternate game on the first visit. Otherwise, their visits will be exactly the same as the BioStream Training Group. Further details on further assessments conducted during the visits can be found in section 4.2

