5.5 Primary Endpoint

Paired-sample t-tests will be used to measure changes from baseline within each group, and independent sample t-tests will be used to measure changes from baseline relative to the alternate game group for all endpoints.

For all endpoints, we will determine whether there were statistically significant changes in scores from baseline or relative to the alternate game group. Significance will be set at $p < 0.05$. Multiplicity of primary endpoints will be managed via statistical corrections.

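### The plan tests every endpoint within arms and between arms and never says the between-arm test decides, so improvement shared by both arms can be reported as a significant primary result

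*Combined protocol and SAP*

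**What the plan says.** The analysis text has two kinds of test. Section 5.5 says "Paired-sample t-tests will be used to measure changes from baseline within each group" and adds independent-sample t-tests on change for the comparison with the alternate game group, for all endpoints. Section 5.7.2 repeats this and concludes: "For all endpoints, we will determine whether there were statistically significant changes in scores from baseline or relative to the alternate game group". The Synopsis (Statistical and Analytic Plan) likewise looks for "observable changes in scores from baseline or relative to the alternate game group and whether these changes are statistically significant". The threshold is p < 0.05, and multiplicity of the primary endpoints is to be handled by an unnamed correction. Section 5.6 applies the same approach to the secondary endpoints.

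The endpoint definitions are narrower. Section 2.1 defines the five primary endpoints as mean change from baseline "based on post-final game play session assessment compared to the alternate game group", and the Synopsis does the same. The objectives are looser: the Synopsis and section 1.1 speak of changes "after engaging in BioStream Training, including in comparison to an alternate game", and the lead sentence of 2.1 also treats the comparison as something included.

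The Supplement to the Statistical Analysis Plan (April 25, 2022) adds 2 × 2 mixed ANOVAs for Ekman-60, SRS and C-JARS. It introduces them with "In addition to the statistical analyses described in the original study protocol", so the paired tests remain.

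**The concern.** The randomised control arm is there to remove whatever happens to both arms: practice on repeated tests, the passage of time, and parents' expectations when they rate the SRS. A paired test in the BioStream arm removes none of these. Section 5.7.2 joins the two kinds of test with an *or* and ranks neither. An author who follows it could therefore report a significant primary result when both arms improved equally.

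A shared shift is plausible in this design. Table 2 gives the Ekman test once at Visit 1 and then lists "Ekman 60 Faces Test | 50 minutes | Subject | Visits 2-6", six administrations in Phase I. The other four primary measures are given five times.

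The multiplicity correction does not help. It limits chance findings, but a shared shift is a real within-arm change, and a stricter threshold only lowers the power to detect it.

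A smaller, conditional point concerns the baseline. Section 5.7.2 analyses subjects randomised at the initial visit who have initial-visit and final-visit data. Section 3.1.4 places the "training session on how to use the alternate game on the first visit", which suggests that the initial visit is Visit 1, while the Synopsis labels Visit 2 as baseline. Entry requires an Ekman score of 75% or less at Visit 1. If that same score served as baseline, regression to the mean would add apparent improvement in both arms.

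**Working it through.** The plan gives no effect size, SD, retest effect or power, so there is no figure of its own to reproduce. The check asks how often a significant result arises when the arms do not differ.

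**Inputs from the documents**
- Up to 150 subjects (5.8) in two randomised groups (3.2, 7.1.1).
- Five primary endpoints (2.1).
- Significance at p < 0.05, with a correction for multiple primary endpoints (5.7.2).

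**Assumptions**
- 1:1 allocation with no dropout, 150/2 = 75 per arm.
- Two-sided tests with Bonferroni over five endpoints, 0.05/5 = 0.01, applied to both kinds of test.
- Normal change scores with SD 1, correlated 0 to 0.3 across endpoints.
- The same true shift *d* (in SD of change) in both arms.

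**Step 1. One paired test.** The statistic is noncentral *t* with *n* − 1 = 74 degrees of freedom and noncentrality *d*√*n*. The two-sided 0.01 critical value is 2.644.

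| *d* | *d*√75 | Chance of significance |
|---|---|---|
| 0.1 | 0.866 | 4.2% |
| 0.2 | 1.732 | 18.9% |
| 0.3 | 2.598 | 48.6% |

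At an uncorrected 0.05 (critical value 1.993) the chance at 0.2 SD is 40% and at 0.3 SD is 73%. The between-arm test on the same data rejects at its nominal rate whatever *d* is, because the shift cancels.

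**Step 2. Five endpoints.** The either-test rule counts a trial if the BioStream paired test or the between-arm test is significant on at least one primary endpoint. There were 20,000 simulated trials per setting.

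| Shift common to both arms | Rule | Correlation 0 | Correlation 0.3 |
|---|---|---|---|
| None | Between-arm only | 5.0% | 4.4% |
| None | Either test | 8.5% | 7.7% |
| 0.1 SD on all five | Either test | 22.2% | 19.8% |
| 0.2 SD on all five | Either test | 66.5% | 56.1% |
| 0.3 SD on all five | Either test | 96.6% | 89.4% |
| 0.2 SD on one only | Either test | 25.2% | 24.3% |
| 0.2 SD on two only | Either test | 38.2% | 36.0% |

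Hand check at correlation 0 and 0.2 SD on all five: the paired tests alone give 1 − (1 − 0.189)^5 = 64.9%, and the between-arm tests add a little to reach 66.5%.

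**Step 3. Sensitivity, 0.2 SD on all five endpoints** (correlation 0 / 0.3)
- Counting only improvements: 65.5% / 54.3%, against about 2.5% for the between-arm tests alone.
- Correcting for all ten tests (0.05/10 = 0.005): 51.6% / 42.8%.
- 60 completers per arm at 0.01: 55.4% / 46.6%.

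**Step 4. The conditional baseline point.** If the Visit 1 Ekman score were the baseline, the expected gain from regression alone is (1 − *r*) × SD × φ(*z*)/Φ(*z*), with *z* = (75 − mean)/SD. Assume an unselected mean of 55 to 70, SD 12 to 15 and retest correlation *r* of 0.6 to 0.9.
- Smallest: mean 55, SD 12, *r* = 0.9 gives 0.13 points.
- Largest: mean 70, SD 15, *r* = 0.6 gives 3.59 points.

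With Visit 2 as baseline this is largely removed.

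**The case against.** The case on the other side is that the intended contrast is clear. The Abstract's aim sets BioStream against the control game without any softening word. Every primary and secondary endpoint is defined relative to the alternate game group. Section 3.1 calls the study a controlled comparison, and 5.7.2 ends by saying, for the secondary endpoints, that the two groups will be compared by t-test. The supplement states that its ANOVAs address between-group differences from pre to post, which in a 2 × 2 design is the interaction. A valid randomised test is therefore planned for every endpoint. No passage calls a within-arm change a success, so the either-test figures describe a rule the plan never states. Under a real shared shift the paired tests also reject their own null correctly.

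Much of this stands. The intent can be inferred, and the percentages illustrate a permitted reading, so they are not a measured error rate of the trial. The 56–67% figure needs a 0.2 SD shift on all five endpoints; with only one shifting it is 24–25%. For SRS, TOVA and both gaze measures Visit 1 cannot be the baseline, because Table 2 schedules them only from Visit 2, so the regression point concerns Ekman alone.

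It does not remove the problem. The sections that should turn the endpoint definition into a decision rule use *or*, and the objectives make the comparison only part of the question. The supplement keeps the original tests, omits TOVA and both primary gaze endpoints, and does not name the interaction as decisive. Inferred intent does not prevent a significant paired test from being reported as a finding.

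**Conclusion.** The concern holds. As written, the plan lets a change common to both arms be presented as a significant result on a primary endpoint, contrary to its own endpoint definitions. If only the between-arm tests decide, the chance of at least one significant primary result with no true difference is about 5%. Under the either-test reading it is about 8% with no shift, 20–22% with a shared 0.1 SD shift and 56–67% with a shared 0.2 SD shift on all five endpoints. These figures rest on 75 per arm, Bonferroni at 0.01, correlation 0 to 0.3 and assumed shifts. The defect in the wording does not depend on them. It bears on the trial's main conclusion, so it must be fixed. The Ekman baseline ambiguity is secondary and matters only if the Visit 1 score is used.

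**What to change.** - **Sections 5.5 and 5.7.2 and the Synopsis.** Replace the sentence that joins the two kinds of test with: *Efficacy on each primary endpoint is concluded only from the between-arm difference in change from baseline (Visit 2). The multiplicity correction is applied to these five tests. Within-arm changes are reported as means with 95% confidence intervals, with no efficacy claim.*
- **Objectives (Synopsis, 1.1, 2.1).** State the aim as change compared with the alternate game, in place of the phrase that merely includes the comparison.
- **Supplement.** Name the Time × Condition interaction as the test. With two time points it equals the equal-variance t-test on change, so it counts as the same test and falls under the same correction.
- **Section 5.7.2, analysis set.** Replace initial-visit data with Visit 2 (baseline) data, and state that the Visit 1 Ekman score is used only for eligibility.

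The cost is wording only, with no new data. The sponsor gives up within-arm p-values as evidence of efficacy. The supplement reports the Ekman ANOVA as already conducted, so the amendment should carry its date and say that it followed at least one analysis.
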